9.5 Study Assessments

9.5.1 Assessments

All assessments and timing of the assessments should be performed according to the Schedule of Procedures and Assessments (Table 1 and Table 2).

9.5.1.1 Demography

Subject demographic information will be collected at the Screening Visit. Demographic information includes date of birth (or age), sex, race/ethnicity.

9.5.1.2 Baseline Assessments

9.5.1.2.1 MEDICAL/SURGICAL AND ACTINIC KERATOSIS HISTORY

Medical and surgical history and current medical conditions will be recorded at Screening (Visit 1). All pertinent medical history must be noted in the CRF/eCRF. A complete AK medical history will also be recorded.

Medical history will include:

- Significant medical and surgical history; childhood diseases and common colds are not required unless it is ongoing at Screening
- A complete AK history from the time of initial diagnosis
- A complete AK treatment history including all commercial and investigational products, including medical therapies and surgical modalities, and other prescribed and nonprescription therapies dating back to the initial diagnosis.

9.5.1.2.2 FITZPATRICK SKIN-TYPE CLASSIFICATION

The Fitzpatrick Skin-Type is a skin classification system¹⁴ which measures 2 components (genetic disposition and reaction to sun exposure). Skin-types range from very fair (Type I) to very dark (Type VI).

Subjects' skin will be typed using this classification system at Screening (Visit 1).

9.5.1.2.3 PRIOR MEDICATIONS

Prior medications taken within 28 days before Day 1, including nonprescription remedies, vitamins, etc, will be recorded at Screening (Visit 1).

9.5.1.2.4 HEIGHT

Height will be measured only during the screening physical examination.

9.5.1.3 Activity Assessments

9.5.1.3.1 ACTINIC KERATOSIS LESION COUNT

The Investigator will perform a count of AK lesions (lesion count) for all subjects at Visits 1 and 2, Visits 7 through 10, and for Day 57 complete responders, also at Visits 11 through 14.

The AK lesion count is the Investigator's assessment of the number of AK lesions in the treatment area. A subject must have 4 to 8 AK lesions in the treatment area to be eligible to continue in the study at Visit 1.

For this assessment, an AK lesion is considered to be on the treatment area, and should be counted if it is completely inside the treatment area or is touching any of the borders of the treatment area. These lesions will be treated during the study medication application process.

The Investigator must NOT refer to any other evaluation to assist with the AK lesion count. This is not a comparison with the AK lesion count at any other timepoint.

9.5.1.4 Pharmacokinetic, Pharmacodynamic, Pharmacogenomic, and Other Biomarker Assessments

9.5.1.4.1 PHARMACOKINETIC ASSESSMENTS

Blood samples (3 mL at each timepoint) for PK analysis of KX2-391 will be collected at the following timepoints (Table 4):

Table 4 Blood Sample Collection Times for Pharmacokinetic Analyses

Application Day	Time (hours)			
	0 predose	0.5 postdose	1 postdose	4 postdose
Window		±5 minutes	±10 minutes	±10 minutes
Both cohorts: Day 1 (Visit 2)	X ^a	X	X	X
Cohort 1: Day 5 (Visit 6)	X ^a	X	X	X
Cohort 2: Day 3 (Visit 4)	X ^a	X	X	X

a Prior to application of study treatment.

Approximately 24 mL will be collected for measurement of plasma concentrations of KX2-391.

The actual times of PK sampling will be recorded.

A description of collection, handling, and shipping procedures for PK samples will be provided to the sites.

Plasma concentrations of KX2-391 will be analyzed to determine C_{max} , and where applicable, AUC_t , C_{min} , and accumulation ratio R.

Plasma concentrations of study drug will be measured using a validated liquid chromatography/tandem mass spectrometry (LC-MS/MS) assay.

9.5.1.4.2 PHARMACODYNAMIC, PHARMACOGENOMIC, AND OTHER BIOMARKER ASSESSMENTS

Not applicable

9.5.1.5 Safety Assessments

Safety assessments will include recording all AEs and serious adverse events (SAEs).

Safety assessments also include laboratory evaluation of hematology, biochemistry, and urinalyses; periodic measurement of weight, vital signs, ECGs, and performance of PEs, as detailed in the sections below and shown in [Table 1](#) and [Table 2](#).

Subjects will be queried for spontaneously reported AEs at each study visit, before assessment of local skin reactions. AEs will be reported separately from LSRs.

Subject-reported LSRs will not be reported as adverse events. Treatments administered for LSRs will be recorded on the Concomitant Medications CRF.

9.5.1.5.1 ADVERSE EVENTS AND OTHER EVENTS OF INTEREST

An AE is any untoward medical occurrence in a patient or clinical investigation subject administered an investigational product. An AE does not necessarily have a causal relationship with the medicinal product. For this study, the study drug is KX2-391 Ointment 1%.

Treatment-emergent AEs are defined as:

- either those AEs with an onset after dosing or
- those pre-existing conditions that worsen after dosing

The criteria for identifying AEs are:

- any unfavorable and unintended sign (including an abnormal laboratory finding), symptom, or disease temporally associated with the use of an investigational product, whether or not considered related to the investigational product
- any new disease or exacerbation of an existing disease
- any deterioration in nonprotocol-required measurements of a laboratory value or other clinical test (eg, ECG or x-ray) that results in symptoms, a change in treatment, or discontinuation from study drug
- recurrence of an intermittent medical condition (eg, headache) not present at baseline

All AEs, regardless of relationship to study drug or procedure, should be collected beginning from the time the subject signs the study ICF through the final contact in the Follow-up Period on Day 57. For subjects participating in the Recurrence Follow-up Period, only AEs at the treatment area will be collected.

Subjects with study drug-related AEs will be followed until resolution, resolved with sequelae, or under medical care. All SAEs must be followed to resolution or, if resolution is unlikely, to stabilization.

All AEs observed during the study will be reported on the CRF/eCRF.

Laboratory Adverse Events

A treatment-emergent abnormal laboratory test result should be considered as a treatment-emergent AE (TEAE) if the identified laboratory abnormality leads to any type of intervention whether prescribed in the protocol or not.

An abnormal laboratory result should be considered by the Investigator to be an AE if it:

- results in the withdrawal of study drug
- results in withholding of study drug pending some investigational outcome
- results in the initiation of an intervention, based on medical evaluation (eg, potassium supplement for hypokalemia)
- results in any out of range laboratory value that in the Investigator's judgment fulfills the definitions of an AE with regard to the subject's medical profile
- increases in severity compared with baseline

Abnormal laboratory values should not be listed as separate AEs if they are considered to be part of the clinical syndrome that is being reported as an AE. It is the responsibility of the Investigator to review all laboratory findings in all subjects and determine if they constitute an AE. Medical and scientific judgment should be exercised in deciding whether an isolated laboratory abnormality should be classified as an AE. Any laboratory abnormality considered to constitute an AE should be reported on the Adverse Event CRF/eCRF.

For significant treatment-emergent laboratory abnormalities meeting criteria as SAEs, the study site must submit an SAE report to the Sponsor or designee using the SAE reporting procedures described in [Section 9.5.3.1](#). However, if a significant treatment-emergent laboratory abnormality is accompanied by, and is part of the syndrome of, a serious clinical event or diagnosis, it is the clinical event/diagnosis that should be reported as the SAE and not the significant treatment-emergent laboratory abnormality.

ECG changes and associated clinical symptoms determined to be clinically significant by the Investigator will be reported as AEs. An ECG abnormality in a subject with symptoms may meet the criteria for an AE as described in this protocol. In these instances, the AE corresponding to the symptomatic ECG abnormality will be recorded on the Adverse Events CRF/eCRF.

For symptomatic ECG abnormalities meeting criteria as SAEs, the study site must submit an SAE report, including the ECG report to the Sponsor, or designee, using the SAE reporting procedures ([Section 9.5.3.1](#)).

Assessing Severity of Adverse Events

Every effort must be made by the Investigator to categorize each AE according to its severity and its relationship to the study treatment.

Adverse events will be graded for severity as follows:

Mild	An event that is easily tolerated by the patient, causing minimal discomfort and not interfering with everyday activities
Moderate	An event that is sufficiently discomforting to interfere with everyday activities

Severe An event that prevents normal everyday activities

Investigators will assess severity for all AEs (for both increasing and decreasing severity). The criteria for assessing severity are different from those used for seriousness (see Section 9.5.1.5.2).

Assessing Relationship to Study Treatment

Items to be considered when assessing the relationship of an AE to the study treatment are:

- temporal relationship of the onset of the event to the initiation of the study treatment
- the course of the event, especially the effect of discontinuation of study treatment or reintroduction of study treatment, as applicable
- whether the event is known to be associated with the study treatment or with other similar treatments
- the presence of risk factors in the study subject known to increase the occurrence of the event
- the presence of nonstudy treatment-related factors that are known to be associated with the occurrence of the event

Classification of Causality

The relationship of each AE to the study drug will be recorded on the CRF/eCRF using the following criteria:

Definitely Related: A clinical event, including laboratory test abnormality, occurring in a plausible time relationship to drug administration, and which cannot be explained by concurrent or underlying disease or other drugs or conditions

Probably Related: A clinical event, including laboratory test abnormality, with a reasonable time sequence to administration of the drug, unlikely to be attributed to concurrent or underlying disease or other drugs or conditions

Possibly Related: A clinical event, including laboratory test abnormality, with a reasonable time sequence to administration of the drug, but which could also be explained by concurrent or underlying disease or other drugs or conditions

Unlikely Related: A clinical event, including laboratory test abnormality, with a temporal relationship to drug administration which makes a causal relationship improbable, and in which other drugs, conditions or concurrent or underlying disease provide plausible explanations

9.5.1.5.2 SERIOUS ADVERSE EVENTS AND OTHER EVENTS OF INTEREST

An SAE is any untoward medical occurrence that at any dose:

- results in death

- is life-threatening (ie, the subject was at immediate risk of death from the AE as it occurred; this does not include an event that, had it occurred in a more severe form or was allowed to continue, might have caused death)
- requires inpatient hospitalization or prolongation of existing hospitalization
- results in persistent or significant disability/incapacity
- is a congenital anomaly/birth defect (in the child of a subject who was exposed to the study drug)

Other important medical events that may not be immediately life-threatening or result in death or hospitalization but, when based on appropriate medical judgment, may jeopardize the subject or may require intervention to prevent one of the outcomes in the definition of SAE listed above should also be considered SAEs. Medical and scientific judgment should be exercised in deciding whether expedited reporting is appropriate in such situations.

In addition to the above, other events of interest, which include pregnancy and overdose, are to be captured using the SAE procedures described in [Section 9.5.3.1](#), but are to be considered as SAEs only if they met one of the above criteria. All events of these types are to be reported on the Adverse Events CRF/eCRF whether or not they meet the criteria for SAEs.

The following hospitalization is not considered to be an SAE because there is no “AE” (ie, there is no untoward medical occurrence) associated with the hospitalization:

- hospitalization planned before informed consent (where the condition requiring the hospitalization has not changed post study drug administration)

All SAEs must be followed to resolution or, if resolution is unlikely, to stabilization.

9.5.1.5.3 LABORATORY MEASUREMENTS

Blood will be collected for clinical laboratory tests at Screening (Visit 1), Day 8 (Visit 7), and Day 57 (Visit 10) ([Table 1](#) and [Table 2](#)). Collection of blood and urine (including samples for pregnancy testing, where applicable) will be conducted at the clinic site. Approximately 20 mL of blood will be collected for clinical laboratory testing, including pregnancy testing, when required. Except for those diagnosed as having diabetes, subjects must be fasted for laboratory assessments. Fasting status must be documented for all laboratory samples.

Microscopic urinalysis will be conducted only when clinically indicated based on dipstick results (laboratory protocol) or as determined by the Investigator. When conducted, microscopic urinalysis results will be recorded on the CRF/eCRF.

The clinical laboratory tests to be measured during the study are provided in [Table 5](#).

Table 5 Clinical Laboratory Tests

Category	Parameters
Hematology	red blood cells (RBC), hemoglobin, hematocrit, platelets, and white blood cells (WBC) with differential (neutrophils, lymphocytes, monocytes, eosinophils, basophils), mean corpuscular volume (MCV), mean corpuscular hemoglobin (MCH), mean corpuscular hemoglobin concentration (MCHC), RBC distribution width (RDW)
Chemistry	
Electrolytes	chloride, potassium, sodium, bicarbonate (HCO ₃)
Liver function tests	alanine aminotransferase (ALT), alkaline phosphatase (ALP), aspartate aminotransferase (AST), gamma glutamyl transpeptidase (GGT), direct bilirubin, total bilirubin
Renal function tests	blood urea/blood urea nitrogen, creatinine
Other	Albumin, calcium, cholesterol, glucose, lactate dehydrogenase (LDH), phosphorus, total protein, triglycerides, uric acid
Urinalysis (dipstick)^a	hydrogen ion concentration (pH), specific gravity, protein, glucose, ketones, leukocyte esterase, nitrite, bilirubin, urobilinogen, blood
Pregnancy Testing	serum pregnancy test, urine pregnancy test (where applicable)

a Microscopic urinalysis will be conducted only when clinically indicated based on dipstick results (laboratory protocol) or as determined by the Investigator.

A laboratory abnormality may meet the criteria to qualify as an AE as described in this protocol (see [Section 9.5.1.5.1](#)). In these instances, the AE corresponding to the laboratory abnormality will be recorded on the Adverse Event CRF/eCRF.

For laboratory abnormalities meeting the criteria of SAEs (see [Section 9.5.1.5.2](#)), the site must electronically transmit the SAE report including the laboratory report to the Sponsor using the SAE form (see [Section 9.5.3.1](#)).

9.5.1.5.4 VITAL SIGNS

Vital sign (pulse rate, systolic and diastolic blood pressure, respiratory rate, and body temperature) measurements will be taken after the subject has been seated for at least 5 minutes at Screening (Visit 1), Day 5 (Visit 6) for Cohort 1 or Day 3 (Visit 4) for Cohort 2, Day 8 (Visit 7), Day 15 (Visit 8), Day 29 (Visit 9), and Day 57 (Visit 10) ([Table 1](#) and [Table 2](#)). Serial vital signs may be obtained to confirm accurate readings.

9.5.1.5.5 PHYSICAL EXAMINATIONS

A complete PE will be performed at Screening (Visit 1) and Day 57 (Visit 10) ([Table 1](#) and [Table 2](#)).

A complete PE will include weight and an assessment of head, eyes, ears, nose, and throat (HEENT), integumentary, gastrointestinal, cardiovascular, respiratory, musculoskeletal, and neurological systems.

Height will be measured only during the screening physical examination.

Documentation of the PE will be included in the source documentation at the site. Only changes from screening PE findings that meet the definition of an AE will be recorded on the Adverse Events CRF/eCRF.

9.5.1.5.6 ELECTROCARDIOGRAMS

A 12-lead ECG will be completed at Screening (Visit 1), Day 8 (Visit 7), and Day 57 (Visit 10) (Table 1 and Table 2), at a convenient time during the visit. ECGs will also be performed in Cohort 2 subjects at 4 hours postdose on Day 1 (Visit 2) and Day 3 (Visit 4). Subjects must be in the recumbent position for a period of 5 minutes prior to the ECG. The ECG data recorded on the CRF/eCRF must include rate, rhythm, intervals, and QTc/QTcF.

ECG changes and associated clinical symptoms determined to be clinically significant by the Investigator will be reported as AEs.

9.5.1.5.7 PREGNANCY TESTING

Serum pregnancy tests will be obtained in females of childbearing potential at Screening (Visit 1), Day 8 (Visit 7), and Day 57 (Visit 10) (Table 1 and Table 2).

A urine pregnancy test will be performed on females of childbearing potential before study medication application on Day 1 (Visit 2). Visit 1 and Visit 2 test results must be reviewed before dosing.

9.5.1.5.8 OTHER ASSESSMENTS

Concomitant Medications

Concomitant medications will be assessed at all clinic visits (Table 1 and Table 2). Any medication (including nonprescription medications) or therapy administered to the subject during the course of the study (starting at the date of informed consent) will be recorded on the Concomitant Medication CRF/eCRF. The Investigator will record any AE on the Adverse Events CRF/eCRF for which the concomitant medication/therapy was administered.

Use of sunblock or any topical products in the treatment area allowed by the Investigator will be recorded in the Concomitant Medication CRF/eCRF.

Local Skin Reactions

At every post-Screening clinic visit through Day 57 (Visit 10), the Investigator or trained designee will assess any LSR on the treatment area for signs:

- Before study medication application (on dosing days)
- After the assessment of adverse events

The LSR assessment is the Investigator's (or trained designee's) assessment of the following signs on the treatment area: erythema, flaking/scaling, crusting, swelling,

vesiculation/pustulation, and erosion/ulceration. These signs will be assessed using a grading scale ranging from 0 (not present) to 4 (worst) (Table 6).

Table 6 Local Skin Reaction Grading Criteria

Grading Criteria					
Local Skin Response	0	1	2	3	4
Erythema	Not present	Slightly pink <50%	Pink or light red >50%	Red, restricted to treatment area	Red extending outside treatment area
Flaking / Scaling	Not present	Isolated scale, specific to lesion	Scale <50%	Scale >50%	Scaling extending outside treatment area
Crusting	Not present	Isolated crusting	Crusting <50%	Crusting >50%	Crusting extending outside treatment area
Swelling	Not present	Slight, lesion specific edema	Palpable edema extending beyond individual lesions	Confluent and/or visible edema	Marked swelling extending outside treatment area
Vesiculation / Pustulation	Not present	Vesicles only	Transudate or pustules, with or without vesicles <50%	Transudate or pustules, with or without vesicles >50%	Transudate or pustules, with or without vesicles extending outside treatment area
Erosion / Ulceration	Not present	Lesion specific erosion	Erosion extending beyond individual lesions	Erosion >50%	Black eschar or ulceration

Examples of LSR signs are shown in photographs in [Appendix 1](#).¹⁵

Application site reactions not classified as LSRs (eg, pruritus, pain, infection) will be reported as adverse events.

All application site reactions and LSRs will be followed to resolution, or if resolution is unlikely, to stabilization.

Treatment for any LSR or interruption/discontinuation of study treatment for an LSR will be recorded on the CRF/eCRF.

LSRs will be reported separately from adverse events.

Pigmentation and Scarring

Hypo- and hyper- pigmentation and scarring on the treatment area will be assessed by the Investigator (or a trained designee) as being present or absent.

Pigmentation and scarring will be assessed at every post-Screening clinic visit through Day 57 (Visit 10) (Table 1 and Table 2). Pigment-related changes or scarring should be followed until resolution or deemed stabilized by the Investigator.

Standardized Photography

Standardized photography will be performed at Screening (Visit 1), Day 1 (Visit 2), Day 8 (Visit 7), Day 57 (Visit 10), and during the Recurrence Follow-up (at 3, 6, 9, and 12 months post-Day 57). Before study medication application on Day 1, the Investigator or a qualified staff member must obtain standardized photography of each subject's treatment area before application of study medication.

Care must be taken to ensure the same lighting, background, subject positioning relative to the camera and camera settings are used for each photograph. Equipment, supplies and detailed instructions for obtaining and managing the photographs will be provided to the investigational center prior to the initiation of subject enrollment.

The photographs are to document the appearance of the subjects' treatment area and to assist with the identification and confirmation of the location of the treatment area throughout the study (Section 9.1.1).

Equipment, supplies and detailed instructions for obtaining and managing the photographs will be provided to the investigational center prior to the initiation of subject enrollment.

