9.7.1.8.2 ADVERSE EVENTS

For AEs, verbatim terms on the CRFs/eCRFs will be mapped to preferred terms (PTs) and system organ classes (SOCs) using the Medical Dictionary for Regulatory Activities (MedDRA; version 16.0 or higher). Subject incidence of AEs will be displayed by SOC. The incidence of AEs will be summarized by cohort. Adverse events will also be summarized by severity, relationship to study drug, and cohort. Subject incidence of SAEs will also be displayed by cohort.

Only those AEs that were treatment-emergent will be included in summary tables. Treatment-emergent AEs are defined as:

- either those AEs with an onset after dosing or
- those pre-existing AEs that worsen after dosing

All AEs, treatment emergent or otherwise, will be presented in subject data listings.

The number (percentage) of subjects with TEAEs leading to death will be summarized by MedDRA SOC, PT, and cohort. A subject data listing of all AEs leading to death will be provided.

The number (percentage) of subjects with TEAEs leading to discontinuation from study drug will be summarized by MedDRA SOC, PT, and cohort. A subject data listing of all AEs leading to discontinuation from study drug will be provided.

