5.2.2 Subject Disposition

For screen failure subjects, a listing will be provided to present their screen failure reasons.

The number of subjects in each analysis set (Safety/Full Analysis, Per-Protocol, Evaluable, and Recurrence Follow-up) will be tabulated by cohort.

For the Safety/Full Analysis Set, subject disposition will be summarized by cohort for:

- Subjects dosed
- Subjects who completed the Day 57 visit
- Subjects who achieved 100% AK clearance at the Day 57 visit
- Subjects who discontinued before the Day 57 visit and their primary reason for discontinuation

In addition, the number of subjects dosed and the number of subjects who completed the Day 57 visit will be summarized by study site and cohort.

A listing of those subjects who discontinued before the Day 57 visit and the associated reasons will be presented.

For the Recurrence Follow-up Set, the recorded discontinuation reasons will be reviewed and subjects who discontinued early due to AK recurrence will be assigned “AK Recurrence” as the new primary reason for discontinuation.

Subject disposition will be summarized by cohort for:

- Subjects who entered the Recurrence Follow-up Period
- Subjects who completed the Recurrence Follow-up Period
- Subjects who discontinued during the Recurrence Follow-up Period and their primary reason for discontinuation

Subjects who discontinued during the Recurrence Follow-up Period will also be listed.

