5.5.1 Adverse Events

All AEs, regardless of relationship to study treatment, will be collected from the time the subject signs the informed consent form through the final contact in the Follow-up Period at Day 57. In addition, treatment-related AEs/SAEs may be followed after the Day 57 visit to resolution, or if resolution is unlikely, to stabilization. For subjects participating in the Recurrence Follow-up Period, all spontaneously reported AEs will be collected whether they occurred at the treatment area or not.

For AEs, verbatim terms on the eCRF will be mapped to system organ classes (SOCs) and preferred terms (PTs) using the Medical Dictionary for Regulatory Activities (MedDRA) version 18.1.

Treatment-emergent AEs (TEAEs) will be identified, and are defined as:

- Either those AEs with an onset on or after the first dose date/time of study treatment
- Those pre-existing AEs that worsen after the first dose date/time of study treatment

If an AE cannot be determined to be treatment-emergent according to the definition above due to partial or missing dates, it will be considered as a TEAE unless it is confirmed to have stopped before the first dose date/time of study treatment.

Furthermore, to identify TEAEs that start before the Recurrence Follow-up Period, AE start dates will be determined relative to the actual Day 57 visit date for the corresponding subject. In such cases, if an AE start date cannot be confirmed to fall within the Recurrence Follow-up Period due to partial or missing dates, that AE will be considered to have started before that period.

An overall summary table of AEs will include the number of subjects with the following events for each cohort.

- Any AEs
- Any TEAEs
- Any AEs that are at least possibly related to study treatment, including those definitely related, probably related and possibly related or those with missing relationship
- Any serious AEs
- Any severe AEs
- Any AEs leading to study discontinuation
- Any AEs that are associated with death

In addition, summaries of the number of subjects with the following AEs will be displayed for each cohort:

- All TEAEs by SOC and PT
- All TEAEs by PT
- All TEAEs by PT and maximum severity (mild, moderate, or severe)
- All AEs that are at least possibly related to study treatment by SOC and PT
- All AEs that are at least possibly related to study treatment by PT

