- All AEs that are at least possibly related to study treatment by PT and maximum severity (mild, moderate or severe)

Severe or serious AEs, whether treatment-emergent or not, will be presented in listings. AEs leading to treatment discontinuation will also be listed.

AEs that are collected during the Recurrence Follow-up Period (i.e. those with start dates after Day 57 visit) will be summarized and listed in the same way, but separately, for the Recurrence Follow-up Set.

Moreover, all AEs will be reviewed manually by the study Medical Monitor to identify any skin cancer-related records. Those event records will be displayed in a separate listing.

All AEs collected during the entire study including the Recurrence Follow-up Period will be presented in a subject data listing.

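### No output described in the SAP counts subjects whose study drug was stopped or interrupted because of a local skin reaction, although the CRF records it

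*Protocol*

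**What the plan says.** **What is collected.** Protocol 9.5.1.5.8: "Treatment for any LSR or interruption/discontinuation of study treatment for an LSR will be recorded on the CRF/eCRF". Drugs given for an LSR are also captured (protocol 9.5.1.5): "Treatments administered for LSRs will be recorded on the Concomitant Medications CRF".

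**How LSRs relate to AEs.** They are kept apart: "Subject-reported LSRs will not be reported as adverse events" (protocol 9.5.1.5) and "LSRs will be reported separately from adverse events" (protocol 9.5.1.5.8).

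**What the protocol planned on stopping drug.** Section 9.7.1.8.2: "The number (percentage) of subjects with TEAEs leading to discontinuation from study drug will be summarized by MedDRA SOC, PT, and cohort", together with a listing.

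**What the SAP plans.** Section 3 says that the SAP replaces the protocol's statistical section. In 5.5.1, the discontinuation row of the overall AE table is "Any AEs leading to study discontinuation". The output on stopping treatment is a listing: "AEs leading to treatment discontinuation will also be listed". In 5.2.2, the disposition table covers "Subjects who discontinued before the Day 57 visit and their primary reason for discontinuation". Section 5.5.2 reports LSR grades in detail but says nothing about action taken on study drug. Section 7, which lists changes from the planned analyses, does not mention the removal of the protocol's study-drug table.

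**The concern.** Leaving the study and stopping the drug are different events. Protocol 9.3.3 treats them as separate decisions, and 9.5.3.2 describes a case in which a subject stops treatment and stays in follow-up. The one discontinuation row in the SAP's AE table counts the first event. The listing covers the second, but for AEs only. A subject whose dosing ends early because of a skin reaction, and who still attends Day 57, is counted under that cause nowhere.

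Safety and tolerability, and the contrast of five with three days of dosing, are secondary objectives. SAP 5.1.2 names LSRs in the secondary safety endpoint. How many subjects could not complete each course because of skin reactions bears directly on that contrast. It also bears on the primary analysis: anyone short of the full course leaves the Evaluable Set, which carries the Day 57 response rate, and the Per-Protocol Set, which carries the lesion counts. The reader would see smaller sets without learning how many subjects were lost to an LSR.

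**Working it through.** The plan states no figure on this point, so there is none to reproduce. The check goes through each planned output that could carry an LSR-driven stop or interruption.

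| Planned output | What it shows | Attributes it to an LSR? |
|---|---|---|
| SAP 5.5.1, overall AE table | AEs that led to leaving the study | No: AEs only, and a different event |
| SAP 5.5.1, listing | AEs that led to stopping treatment | No: AEs only |
| Protocol 9.7.1.8.2, table (superseded) | TEAEs that led to stopping study drug | No: TEAEs only |
| SAP 5.5.2 | LSR grades by visit, worst grade, shifts, composite score, listed comments | No count of action on study drug |
| SAP 5.2.6.1 | Doses received | No: no reason given |
| SAP 5.2.6.2 | Doses received divided by 5 or 3 | No: no reason given |
| SAP 5.2.2, analysis-set sizes | Drop from Safety/Full to Per-Protocol and Evaluable | No: no reason given |
| SAP 5.2.2, disposition | Leaving before Day 57, with primary reason | Only if the subject leaves and the recorded reason says so |
| SAP 5.2.5.1 | Concomitant drugs by class and name | No: not by reason for use |

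No row gives the count. Restoring the protocol's table would not supply it either, because that table covers TEAEs only. The missing LSR count and the undeclared loss of the TEAE table are therefore two separate gaps.

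**How visible would such stops be in the compliance table?** The inputs are about 80 enrolled per cohort (protocol 9.1) and planned doses p of 5 or 3 (SAP 5.2.6.2). The number of stoppers k and the doses they received r are assumptions, because the documents give no rate. Assume that 5% stop, with a range of 0 to 10%: 0.05 × 80 = 4, range 0 to 8. One subject is 1/80 = 1.25 points.

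Mean compliance = 1 − (k/80) × (1 − r/p), with everyone else fully dosed.

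| k | Cohort 1, r/p = 3/5 | Cohort 2, r/p = 2/3 |
|---|---|---|
| 1 | 1 − 0.0125 × 0.4 = 99.5% | 1 − 0.0125 × 0.333 = 99.6% |
| 4 | 1 − 0.05 × 0.4 = 98.0% | 1 − 0.05 × 0.333 = 98.3% |
| 8 | 1 − 0.10 × 0.4 = 96.0% | 1 − 0.10 × 0.333 = 96.7% |

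The median is 100% in every case. The minimum is 60% in Cohort 1 and 67% in Cohort 2. The missed doses do show, but weakly: the minimum says that at least one subject stopped early, not how many did or why.

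**The case against.** A reader might infer that these events enter no table at all, or that LSR tolerability is invisible. The documents do not support that. Missed doses feed the exposure, compliance and analysis-set summaries. SAP 5.5.2 tabulates LSR severity by sign, visit and cohort and lists the comments. Pain, pruritus and infection at the application site are AEs, so a stop for one of those is an AE stop. Keeping LSRs separate from AEs is a deliberate design choice. What is missing is the attribution of a stop to an LSR.

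A reader might also infer that every such subject escapes the disposition table. That too goes too far. Protocol 9.5.4 encourages subjects who withdraw from treatment to complete the Early Termination assessments, and 9.3.3 requires the reason to be documented. Some would therefore leave before Day 57 and appear in disposition. This narrows the gap without closing it. Section 9.3.3 allows treatment to stop without study exit, and its list of reasons has no LSR category, so a stop could be filed under another heading. The sponsor met a similar problem with AK recurrence, which was not a discontinuation event on the CRF, and recategorised those subjects (SAP section 7). The SAP makes no such provision for LSRs.

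Two limits stand in full. The documents give no rate of LSR-driven stops, and protocol 9.4.4 describes the preliminary forearm experience with LSRs as acceptable. The mock tables and dataset specifications are separate documents that were not available, so an output defined only there cannot be excluded.

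**Conclusion.** The point holds in this form. The CRF captures drug stopped or interrupted for an LSR, and no output described in the SAP counts it. The AE-based outputs omit it by rule, unless a site also records the event as an AE. In addition, the SAP reduces a planned table on stopping study drug to a listing without declaring the change.

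The size cannot be derived from the documents. The figures of 4 of 80 (range 0 to 8) rest on an assumed rate, and the true count may be zero. Two stronger readings are not supported: that the trial would report these stops as none, since the plan leaves them unreported by cause rather than reporting a zero; and that they are the main tolerability failure, since no rate is given. No power figure or decision rule is shown to change, and the SAP describes the cohort contrast as mainly noninferential. This is a cheap improvement to the safety reporting.

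**What to change.** In SAP 5.5, add one table by cohort in the Safety/Full Analysis Set. It gives the number and percentage of subjects with study drug interrupted, and separately with study drug discontinued, (a) for an LSR, (b) for a TEAE, (c) for either. Add a listing with the sign, grade and study day.

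In the overall AE table of SAP 5.5.1, put AEs that led to stopping study drug on their own line, as protocol 9.7.1.8.2 intended, and keep AEs that led to leaving the study on another. If the protocol's SOC and PT table is not restored, declare its removal in SAP section 7.

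The cost is one small table, one listing and one line. The protocol already requires the LSR information on the CRF, so no new data collection is needed. The downside is a tolerability figure that may look less favourable. If the count is zero, stating it would still inform the contrast between regimens.
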